## Objectives

- Primary Objectives
  - Validate patient tolerability of needle-free delivery of intralesional triamcinolone using patient-reported outcome measures.
- Secondary Objectives
  - Validate efficacy of needle-free delivery of intralesional triamcinolone for pediatric alopecia areata.
  - Assess the impact of needle-free delivery of intralesional triamcinolone on quality of life for pediatric alopecia areata.

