## Background

Alopecia areata (AA) is a significant medical condition that causes emotional and psychosocial distress as well as reductions in quality of life, especially in the pediatric population [Aldhouse et al 2020; Mostaghimi 2021; Christensen et al 2017]. When limited and patchy, an estimated 80% of those affected will see spontaneous recovery; however, this disease is characterized by frequent remittances and relapses and may progress to more severe disease – alopecia totalis or alopecia universalis (Ito 2012; Barton 2021). Currently, there are no Food and Drug Administration- (FDA) approved treatments for pediatric alopecia areata, and there is a paucity of well-designed, randomized-controlled clinical trials (Meah et al 2020; Barton et al. 2021). Current recommendations, however, support the use of intralesional triamcinolone acetonide (ILTA) in adults (Meah et al 2020, Yee et al 2019), and pediatric patients (Barton et al. 2021; Fernando et al. 2020; Wang et al. 2012).

The use of ILTA in the pediatric population is often limited due to fear of injections and pain [Hordinsky 2015]. A 2002 chart review by Tan et al. demonstrated >50% improvement in 65% of pediatric patients at 12 weeks with use of ILTA, but >10% of patients dropped out of the study due to pain (Tan et al 2002). Current methods for pain mitigation include small gauge needles, cold sprays, distraction, and topical anesthetics, each with their own limitations (Want et al. 2012). Controlling pain is important as it can result in several physiological, psychological, and emotional consequences such as hypoxemia, vasovagal reaction, tachycardia, life-long needle phobia, fear of other procedures, higher levels of pain during other procedures, and possible avoidance of the healthcare system as adults (Ballard et al 2018; Birnie et al 2018). Given limited treatment options for pediatric patients with AA, ameliorating the fear and pain associated with needle-based ILTA is preferable, and the Med-Jet injector may be a device that can do just that. If well-tolerated, well-designed, randomized clinical trials may be feasible in the pediatric population.

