## **Inclusion and Exclusion Criteria**

	Inclusion Criteria					
	Subjects must meet all of the following criteria to be eligible for this study:	Yes	No			
1	6-17 years of age.					
2	Diagnosed with alopecia areata by either: • A board-certified dermatologist, OR • Dermatology Nurse Practitioner, OR • Skin punch biopsy					
3	
 
Patient has at least 2 alopecic patches each measuring at least 2 cm^2 and are
 
Located on contralateral body sites OR
 
Within the same body site but separated by ≥ 1 cm
 
					
4	Patient is a candidate for intralesional triamcinolone.					
4	Patient able to give informed assent under IRB approval procedures when appropriate.					
5	At least one parent or guardian is able to provide informed consent.					

	Exclusion Criteria				
	A patient who meets any of the following criteria will be excluded from the study.	Yes	No		
1	Patient has alopecia totalis, alopecia universalis, or alopecia areata with ophiasis pattern.				
2	Known allergy or hypersensitivity to triamcinolone acetonide				
3	Pregnant, breastfeeding, or planning to get pregnant 4 weeks before, during, and 4 weeks after the study.				
4	Patient is unable/unwilling to provide informed assent when applicable.				
5	Known medical diagnosis or use of a medication that alters pain response at time of injection.				
6	Active infection at site designated for injection.				
7	If currently being treated for alopecia areata, the current treatment regimen has been started within less than 4 weeks of screening.				

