## **Prior and Concomitant Medications and Therapies**

All medications and therapies being taken/used by the subject at the time of consent or at any time during the study will be recorded. All medications and therapies for alopecia areata, will be recorded. The stop dates and reason for stopping all medications and therapies prohibited in the study will be recorded.

- Intervention
  - At least two patches; each measuring 2 cm2 and at least 1 cm from one another will be identified, mapped out, and photographed.
  - Only one of the alopecic patches will be treated.
  - The concentration of ILTA will be controlled at up to 1 mg per cubic centimeter (0.1 ml
     @ a maximum concentration of 10mg/ml) injected every 1 cm until patch has been fully treated. The researcher providing treatment will be properly trained to deliver intradermal injections using the syringe and needle-free system.
  - Med-Jet with Triamcinolone (TAC) Procedure ILTA will be administered into the patches. The PI and co-investigators will be performing interventions and follow proper training by the manufacturer on operation and handling of the device. Training will consist of a live course with a designated manufacturer technician supplemented with training videos. A standard sterile disposable 5 ml syringe will be used to draw TAC using standard sterile protocol. This syringe will be attached to the Med-Jet along with a sterile barrel and disposable sterile tip. The target lesion will be wiped with alcohol and injected with up to 10mg/ml of TAC directed towards the dermis to create a blanching wheal that is 1 cubic centimeter (total of 0.1 ml of injected fluid). The optimal injection pressure used on the subject will start at 130 pounds per square inch (psi) and increased by 5 psi until a blanching wheal is observed. The optimal pressure until the targeted patch is completely treated.
  - Patients will be treated at each visit unless complete regrowth has occurred.
     Photographs will be taken at each visit and activities will be completed as above.

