#### **Clinical Assessments**

- Physician Efficacy Assessments
  - Severity of Alopecia Tool (SALT) Score The SALT score is a visual tool to help assess percentage of hair loss on the scalp. The scalp is divided into four sections top, back, right side, and left side. Each section contributes to a total of 100% (i.e. top = 40%, back = 24%, sides = 18% each). Raters assess total percentage of hair loss in the section and then multiple is by the respective multiplier which is based on that sections total percentage of the scalp 40%, 24%, or 18%. Only terminal hairs are considered hair growth in this tool. (Olsen et al. 2004) Figure 1 illustrates the visual aid and allows for intuitive use. This is a static tool and only quantifies the hair loss at one point in time.
  - Alopecia Areata Investigator Global Assessment (AA-IGA) The AA-IGA categorizes the scalp hair loss into 5 categories based on the SALT score. The five categories are: 1 = None, 2 = Limited, 3 = Moderate, 4 = Severe, and 5 = Very Severe. The corresponding SALT scores for each category are: 1 = 0%, 2 = 1-20%, 3 = 21-49%, 4 = 50-94%, and 5 = > 95%. This is a static tool and only quantifies the hair loss at one point in time (Olsen 2004).
  - "Rule of Thumb" Assessment and Regrowth Categorization A patient's thumbprint projection is approximately 1% of the scalp surface area (King 2019). When selecting the alopecic patch for treatment and its comparator, thumb projections will be used to quantify the percentage of total scalp hair loss contributed by each these patches at baseline. At each subsequent visit, the thumbprint projection from baseline will be used to determine percent of regrowth since baseline. Based on regrowth, the patient will be categorized into one of 6 categories: A0-5. Where A0 = no change or further loss, A1 = 1-24% regrowth, A2 = 25-49% regrowth, A3 = 50-74% regrowth, A4 = 75-99% regrowth, and A5 = 100% regrowth.
- Patient-Reported Efficacy Assessments
  - Patient-Reported Hair Loss Whole Scalp This assessment will apply to the subject's whole scalp surface area. This question will be asked at every visit. And it will include 5 numerical categories: 0 = No missing hair (0% of my scalp is missing hair; I have a full head of hair); 1 = limited area (1% to 20% of my scalp is missing hair); 2 = moderate area (21% to 49% of my scalp is missing hair); 3 = large area (50% to 94% of my scalp is missing hair); and 4 = Nearly all or all (95% to 100% of my scalp is missing hair).

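### With one patch treated per child and no control group of children, changes in whole-scalp scores, CDLQI and T-QoL cannot be attributed to the injections; the treated-versus-comparator patch contrast should carry the efficacy claim

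*Combined protocol and SAP*

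**What the plan says.** **Treatment.** The entry criterion reads "Patient has at least 2 alopecic patches each measuring at least 2 cm" (square centimetres), with no upper limit on number. The Intervention text, under Prior and Concomitant Medications and Therapies, says "Only one of the alopecic patches will be treated". The device procedure a few lines later has the drug given into patches, in the plural.

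**Aims.** Two secondary objectives are causal in wording: "Validate efficacy of needle-free delivery of intralesional triamcinolone for pediatric alopecia areata" and "Assess the impact of needle-free delivery of intralesional triamcinolone on quality of life for pediatric alopecia areata". The hypothesis in Study Design likewise expects efficacy and a favourable effect on quality of life.

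**Measures.** Clinical Assessments lists these as efficacy assessments:
- SALT, which scores the whole scalp.
- AA-IGA: "The AA-IGA categorizes the scalp hair loss into 5 categories based on the SALT score".
- Patient-reported hair loss: "This assessment will apply to the subject's whole scalp surface area".
- A 5-point patient regrowth rating, asked for the whole scalp and separately for the selected patches.
- A thumbprint measure of the treated patch and a comparator patch, converted to a regrowth category A0-A5 that is assigned to the patient.

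Quality of life is one CDLQI or T-QoL score per child per visit. Data to be Collected also counts the patient survey as quality-of-life data. Patient Survey describes it as covering tolerability, comfort, fear and preference relative to needle and syringe.

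**Disease course.** Background says "When limited and patchy, an estimated 80% of those affected will see spontaneous recovery", without a time frame, and adds that "this disease is characterized by frequent remittances and relapses and may progress to more severe disease". Exclusion criterion 7 allows existing alopecia treatment that was not begun in the 4 weeks before screening.

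**Analysis.** The Data Analysis Plan names no efficacy or quality-of-life endpoint and no contrast between patches.

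**The concern.** The intervention acts on one patch, but most of the listed outcomes describe the whole scalp or the whole child. With no untreated or needle-treated children, nothing shows what those outcomes would have done without the injections. Three other causes are named or permitted in the protocol: spontaneous recovery, relapse or progression, and continuing background treatment.

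The error can run either way. Regrowth of untreated patches could be reported as efficacy or as better quality of life due to the treatment. New loss elsewhere, or simple dilution, could hide a real effect in the treated patch. Since the analysis plan ties no measure to the efficacy or quality-of-life aim, nothing in it prevents either misreading from reaching the design of the later trials this pilot is meant to inform.

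**Working it through.** **No plan figure to reproduce.** The sample size of 15 (Number of Research Participants) rests on the pilot nature of the study and earlier pain scores. No formula, SD or power is given, and nothing is sized for efficacy or quality of life.

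**1. Dilution.** Let S be baseline SALT and t the treated patch's share of the scalp. If that patch regrows fully and nothing else changes, SALT becomes S − t, a relative fall of t/S. AA-IGA bands (Clinical Assessments): category 1 = 0%, 2 = 1-20%, 3 = 21-49%. Patch sizes are assumed, and all patches are taken to be on the scalp.

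| S (%) | t (%) | S − t (%) | t/S | AA-IGA |
|---|---|---|---|---|
| 2 | 1 | 1 | 50% | 2 to 2 |
| 5 | 1 | 4 | 20% | 2 to 2 |
| 10 | 2 | 8 | 20% | 2 to 2 |
| 10 | 5 | 5 | 50% | 2 to 2 |
| 20 | 5 | 15 | 25% | 2 to 2 |
| 22 | 1 | 21 | 5% | 3 to 3 |
| 22 | 5 | 17 | 23% | 3 to 2 |
| 40 | 10 | 30 | 25% | 3 to 3 |

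While another scalp patch of at least 1% remains, AA-IGA cannot reach category 1, however well the treated patch responds.

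**2. Mimicry.** Suppose the injections have no effect and a proportion p of children recover within 12 weeks. The expected number is 15p, and the chance that at least 8 recover is a binomial tail. The protocol gives no 12-week value of p, so a range is shown; 80% is its untimed figure.

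| p | 15p | P(at least 8 of 15) |
|---|---|---|
| 0.20 | 3.0 | 0.004 |
| 0.50 | 7.5 | 0.50 |
| 0.65 | 9.75 | 0.89 |
| 0.80 | 12.0 | 0.996 |

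The range is too wide to size the bias. It does show that whole-scalp recovery in half the children may be unremarkable without any treatment effect.

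**3. Would a historical benchmark help?** If 80% were taken as the 12-week rate, 15 of 15 recoveries would have probability 0.80^15 = 0.035, and at least 14 of 15 would have 0.167. Only unanimous recovery would pass a one-sided 0.05 test. With an assumed true rate of 95%, the chance of that is 0.95^15 = 0.46.

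**4. Which measures have a control?**
- *SALT, AA-IGA, both whole-scalp patient ratings, CDLQI, T-QoL:* none. The untreated patch is part of the score or of the child's overall experience, so it cannot serve as a comparator.
- *Thumbprint regrowth and patient rating of the selected patches:* yes, the comparator patch in the same child.
- *Patient survey:* its items concern the procedure, so regrowth elsewhere does not directly confound them.

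**5. Is the paired contrast usable with 15 children?** With a two-sided sign test on which patch regrew more, p = 2 × 0.5^m when all m untied children favour the treated patch. For m = 5, p = 0.0625; for m = 6, p = 0.031. Six untied children in one direction are enough. The two tests that the Data Analysis Plan mentions, χ² and Mann-Whitney, assume independent groups and do not use the pairing.

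**The case against.** The strongest reply is that the protocol already provides a within-child comparator patch, measured by both physician and patient. That stands, and it rules out a reading some may be tempted by, namely that efficacy cannot be assessed at all. It does not rescue the whole-scalp or child-level scores.

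Other replies also carry weight:

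- *Quality of life is not wholly without sound data.* A reader might infer that it is. The patient survey, which the protocol lists as quality-of-life data, is about the procedure and is not directly affected. CDLQI and T-QoL remain uncontrolled.
- *Improvement need not be mostly spontaneous.* A reader might infer that it would be. The documents give neither the 12-week remission rate nor patch shares, and background treatment is another possible cause.
- *The 65% and 80% figures in Background cannot be ranked.* One is more than 50% improvement at 12 weeks in a chart review of needle-treated children. The other is recovery with no time frame. They do not show that injection does worse than no treatment.
- *AA-IGA is coarse in any case.* A fall from 10% to 2% also stays in category 2, so part of its insensitivity is banding rather than untreated patches.
- *The study is a pilot, these aims are secondary, and no causal test of these scores is planned.* This limits the seriousness. It does not make a causal reading of an uncontrolled score sound, and the objectives invite that reading.

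**Conclusion.** The concern holds for SALT, AA-IGA, the two whole-scalp patient ratings, CDLQI and T-QoL. Changes in these cannot be separated from remission, relapse or permitted background treatment, so they support no statement that the injections worked or improved quality of life. The direction of any net bias is unknown and its size cannot be given; the tables above are illustrations under assumed patch sizes and recovery rates.

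The treated-versus-comparator patch data are the only within-child control for efficacy. A rating of the treated patch alone would face the same remission problem. The contrast has its own limits: the protocol does not describe the choice of patch as randomised or the rating as blinded, and A0-A5 is assigned to the patient.

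The dilution argument and the comparator both depend on the one-patch sentence, which conflicts with the plural wording nearby. The lack of a control group of children does not depend on it. The primary pain objective is unaffected.

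**What to change.** 1. **Data Analysis Plan:** name the paired within-child contrast of regrowth, treated versus comparator patch, as the efficacy analysis, using a paired method.
2. **Clinical Assessments:** record A0-A5 for each patch rather than for the patient, and state how the treated patch is chosen.
3. **Clinical Assessments and Data Analysis Plan:** label SALT, AA-IGA and both whole-scalp patient ratings as descriptions of disease course.
4. **Objectives and Study Design:** reword the quality-of-life aim and the matching hypothesis to describing quality of life during the study. Report CDLQI and T-QoL changes with no causal claim, and report the procedure-focused survey separately.
5. **Intervention:** reconcile the statement that one patch is treated with the statement that the drug is given into patches.

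**Cost:** wording changes and one regrowth category per patch instead of one per child, from thumbprint measurements that already cover both patches at baseline. No added visits, procedures or children. The downside is a weaker secondary claim.

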## Safety Assessments

- Full Skin Exam/Limited Skin Exams/ Photographs A full skin examination includes evaluation of all cutaneous and mucosal surfaces. A limited skin exam includes only evaluation of the scalp. Photographs of affected skin will be completed each visit. Patient can decline examination of breasts, buttocks, and genitals during the full skin exam.
- **Pregnancy Surveillance & Contraception Education** Subjects of childbearing potential will require a urine pregnancy test at each visit.
- Monitoring Adverse Events Details of adverse event reporting may be found in section 6.

#### **Clinical Assessments**

- Physician Efficacy Assessments
  - Severity of Alopecia Tool (SALT) Score The SALT score is a visual tool to help assess percentage of hair loss on the scalp. The scalp is divided into four sections top, back, right side, and left side. Each section contributes to a total of 100% (i.e. top = 40%, back = 24%, sides = 18% each). Raters assess total percentage of hair loss in the section and then multiple is by the respective multiplier which is based on that sections total percentage of the scalp 40%, 24%, or 18%. Only terminal hairs are considered hair growth in this tool. (Olsen et al. 2004) Figure 1 illustrates the visual aid and allows for intuitive use. This is a static tool and only quantifies the hair loss at one point in time.
  - Alopecia Areata Investigator Global Assessment (AA-IGA) The AA-IGA categorizes the scalp hair loss into 5 categories based on the SALT score. The five categories are: 1 = None, 2 = Limited, 3 = Moderate, 4 = Severe, and 5 = Very Severe. The corresponding SALT scores for each category are: 1 = 0%, 2 = 1-20%, 3 = 21-49%, 4 = 50-94%, and 5 = > 95%. This is a static tool and only quantifies the hair loss at one point in time (Olsen 2004).
  - "Rule of Thumb" Assessment and Regrowth Categorization A patient's thumbprint projection is approximately 1% of the scalp surface area (King 2019). When selecting the alopecic patch for treatment and its comparator, thumb projections will be used to quantify the percentage of total scalp hair loss contributed by each these patches at baseline. At each subsequent visit, the thumbprint projection from baseline will be used to determine percent of regrowth since baseline. Based on regrowth, the patient will be categorized into one of 6 categories: A0-5. Where A0 = no change or further loss, A1 = 1-24% regrowth, A2 = 25-49% regrowth, A3 = 50-74% regrowth, A4 = 75-99% regrowth, and A5 = 100% regrowth.
- Patient-Reported Efficacy Assessments
  - Patient-Reported Hair Loss Whole Scalp This assessment will apply to the subject's whole scalp surface area. This question will be asked at every visit. And it will include 5 numerical categories: 0 = No missing hair (0% of my scalp is missing hair; I have a full head of hair); 1 = limited area (1% to 20% of my scalp is missing hair); 2 = moderate area (21% to 49% of my scalp is missing hair); 3 = large area (50% to 94% of my scalp is missing hair); and 4 = Nearly all or all (95% to 100% of my scalp is missing hair).
  - 5-Point Patient-Reported Regrowth Whole Scalp and Selected Patches At each visit after the baseline visit, the subject will be asked about their perceived amount of hair regrowth both for the whole scalp and those patches selected at baseline. The subject will be able to select one of 5 categories: 1 = Further Loss, 2 = No Change, 3 = A Little Improved (<50% regrowth), 4= A lot of improvement (50-99% regrowth), and 5= Complete Regrowth (100%).

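### The plan gives no rule for reading fractions of a thumbprint, and for patches near the 2 cm² entry floor the thumbprint cannot reliably separate regrowth grades A1 to A4

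*Combined protocol and SAP*

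**What the plan says.** The Rule of Thumb paragraph under Clinical Assessments fixes the unit: "A patient's thumbprint projection is approximately 1% of the scalp surface area". At baseline, "thumb projections will be used to quantify the percentage of total scalp hair loss contributed by each these patches at baseline". For follow-up it says "At each subsequent visit, the thumbprint projection from baseline will be used to determine percent of regrowth since baseline". A0 means no change or further loss, and the other grades are "A1 = 1-24% regrowth, A2 = 25-49% regrowth, A3 = 50-74% regrowth, A4 = 75-99% regrowth, and A5 = 100% regrowth".

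Inclusion criterion 3 sets the smallest eligible patch: "Patient has at least 2 alopecic patches each measuring at least 2 cm" (squared). The Intervention text under Prior and Concomitant Medications and Therapies gives the same size, "At least two patches; each measuring 2 cm2 and at least 1 cm from one another", and adds that these patches "will be identified, mapped out, and photographed". The Study Timeline schedules photographs at Weeks 0, 4, 8 and 12.

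The documents give no scalp or thumbprint area in cm². They do not say whether projections are counted whole, read in fractions, or used only as a reference for judging regrowth by eye. They specify no patch measurement in cm² after entry.

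**The concern.** One percent of the scalp is a natural unit for how much of the whole scalp is affected. Here it must also resolve quarter-steps of change within one patch, and the entry floor admits patches that may be smaller than the unit itself. With no reading rule, two raters, or one rater on two patches of the same child, could turn the same appearance into different percentages.

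This grade is the only physician-rated measure at patch level, because SALT and AA-IGA describe the whole scalp. The study has 15 subjects and treats only one patch in each. A few patches graded wrongly because of the unit could blur a real difference between treated and comparator patches, or make an unchanged patch look partly regrown.

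**Working it through.** **Inputs from the protocol.** Thumbprint = about 1% of scalp area (Clinical Assessments). Smallest patch = 2 cm² (inclusion criterion 3; Intervention text). Grade cut-points = 1, 25, 50, 75 and 100%. The 1% is the plan's only figure on this point. It cannot be converted to cm² from the documents, so there is nothing further to reproduce.

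**Assumptions.** Scalp area S is not given; 300 to 700 cm² is used as a range. The reading error is also assumed, as stated in step 3.

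**1. Patch size in thumbprints.** One thumbprint is 0.01 × S cm², so a 2 cm² patch is b = 2 / (0.01 × S) thumbprints. It equals one thumbprint at S = 2 / 0.01 = 200 cm² and is smaller for any larger scalp. One 25-point band of the patch is 0.25 × 2 = 0.5 cm².

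| S (cm²) | Thumbprint (cm²) | 2 cm² patch (thumbprints) | 25-point band (thumbprints) |
|---|---|---|---|
| 200 | 2 | 1.00 | 0.25 |
| 300 | 3 | 0.67 | 0.17 |
| 400 | 4 | 0.50 | 0.13 |
| 500 | 5 | 0.40 | 0.10 |
| 700 | 7 | 0.29 | 0.07 |

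**2. Grades reachable by counting.** A baseline of k counting units allows regrowth values of 0/k, 1/k, …, k/k.
- k = 1 gives A0 and A5.
- k = 2 gives A0, A3 and A5.
- k = 3 gives A0, A2, A3 and A5.
- k = 4 gives all but A1.
- k = 5 or more gives all six.

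For a 2 cm² patch:
- Whole thumbprints: at S = 300 the baseline rounds to 1, so only A0 and A5 are possible. Above S = 400 it rounds to 0 and percent regrowth is undefined. S = 400 is a rounding tie.
- Half thumbprints: for S from 300 to 700 the baseline is one unit, so only A0 and A5 are possible. The patch reads as complete once less than 0.25 thumbprint is hairless. That is 0.75 cm² at S = 300, or true regrowth above 1 − 0.75/2 = 62.5%. At S = 700 it is 1.75 cm², or true regrowth above 1 − 1.75/2 = 12.5%.
- Quarter thumbprints: three units at S = 300, two at 400 and 500, and one at 700, so two to four of the six grades are reachable.

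By whole count, all six grades need 5 × 0.01 × S: 15 cm² at S = 300 and 35 cm² at S = 700. By quarter count the figures are 3.75 and 8.75 cm².

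**3. Continuous reading with error.** Suppose fractions are read freely, with independent normal error of SD 0.1 thumbprint at each visit (assumed) and no true change. The patch is graded A2 or better when b + e₁ ≤ 0.75 × (b + e₀), that is, e₁ − 0.75e₀ ≤ −0.25b. The left side has SD 0.1 × √(1 + 0.75²) = 0.125. The probability is therefore Φ(−0.25b / 0.125) = Φ(−2b).

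| Patch | S = 300 | S = 400 | S = 700 |
|---|---|---|---|
| 2 cm² | Φ(−1.33) = 9% | Φ(−1.00) = 16% | Φ(−0.57) = 28% |
| 4 cm² | Φ(−2.67) = 0.4% | Φ(−2.00) = 2% | Φ(−1.14) = 13% |

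With the error held fixed, doubling the patch sharply reduces the problem.

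**4. What direct area reading would need to achieve.** For a 2 cm² patch read with SD s cm², the same formula gives Φ(−0.5 / (1.25s)) = Φ(−0.4/s). An SD of 0.1 thumbprint corresponds to 0.3 to 0.7 cm², which returns the 9% and 28% above. An SD of 0.2 cm² would give Φ(−2) = 2%, and 0.1 cm² would give Φ(−4), below 0.01%. These SDs are illustrations; the documents give none.

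**The case against.** The strongest reply is that the protocol contains no rounding rule, so coarse counting is imposed on it by the reader. The text also fits using the baseline projection as a fixed reference and judging regrowth against it by eye. All six grades are then available, so a reader who infers that A1 to A4 are impossible as written goes beyond the documents. That stands. What remains is that judging by eye has no stated method or precision, and the thumbprint then contributes little to the percentage.

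Second, that every small patch is below one thumbprint is not established. It depends on a scalp above 200 cm², and 2 cm² is a floor with no stated distribution of patch sizes. How many of the 15 subjects would be affected is unknown. That stands too.

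Third, a reader might infer that every comparison of treated with comparator patch rests on this grade. It does not. Subjects also report "perceived amount of hair regrowth both for the whole scalp and those patches selected at baseline", and photographs are taken. The patient item is coarser, however, with one band below 50% and one for 50–99%. The Data Analysis Plan names no test of treated against comparator patches, so harm to a specific planned analysis cannot be claimed.

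Fourth, more dramatic error rates are easy to produce but say little. If regrowth is taken as uniform on 0–100%, almost no true values are A0 or A5, so any reading limited to 0% or 100% is wrong nearly always by construction. Likewise, A1 starts at 1%, so any symmetric error puts almost half of unchanged patches in A1 or better. A direct area reading of a 2 cm² patch with SD 0.1 cm² would still give 44%: Φ(−0.02 / (0.1 × √(1 + 0.99²))). Neither figure counts against the thumbprint in particular.

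**Conclusion.** The point holds as a limited one. The plan derives single-patch regrowth from a unit of about 1% of the scalp, sets no rule for fractions of that unit, and admits patches from 2 cm². Near that floor the unit cannot reliably separate A1 to A4. If thumbprints are counted whole or by halves, at most A0 or A5 remains. If they are read continuously, an unchanged 2 cm² patch would be graded A2 or better 9% to 28% of the time. Both results assume a scalp of 300 to 700 cm², and the second also assumes a reading SD of 0.1 thumbprint.

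The documents do not show that the A0–A5 scale is too coarse in general, nor that most enrolled patches would be misgraded. The measure serves a secondary objective of a proof-of-concept pilot whose primary objective is tolerability. The change is worth making because it is cheap and the material for it is already being collected.

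**What to change.** In the Rule of Thumb paragraph, keep the thumbprint to describe each selected patch's share of the scalp at baseline. For follow-up, define:

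percent regrowth = 100 × (baseline area − current area) / baseline area,

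where area is the part of the patch lacking terminal hair, in cm². Take it from the mapped outline, or from the scheduled photograph with a ruler in frame. Use the same method for the treated and the comparator patch at Weeks 0, 4, 8 and 12, and assign A0 to A5 from the resulting percentage. Analysing the continuous percentage as well is optional.

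The cost is a wording change, a ruler in photographs already planned, and at most 15 × 2 × 4 = 120 area readings, which means a few minutes per visit. No visit or procedure is added. Area reading shares the thumbprint's difficulties with scalp curvature and sparse regrowth, so one sentence on how sparse hair inside the outline is treated would help. At the 2 cm² floor, the gain depends on reading area more precisely than the 0.3 to 0.7 cm² that 0.1 thumbprint represents.
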